2.2.2 Safety Data

AZD6244 Hydrogen-Sulfate Capsule

Safety data from a phase 1 study of the Hyd-Sulfate capsule formulation are available at dose levels of 25 mg BID (n=6), 50 mg BID (n=7), 75 mg BID (n=7), and 100 mg BID (n=8). One DLT was reported in the first 22 days of dosing in the 75 mg BID cohort (CTCAE grade 3 fatigue that resolved with discontinuation of drug). Two DLTs (pleural effusion and rash, both CTCAE grade 3) were reported in the first 22 days of dosing in the 100 mg BID cohort. The MTD of selumetinib Hyd-Sulfate capsule was determined to be 75 mg BID.

The most frequently reported adverse events were fatigue, dermatitis acneiform, nausea, diarrhea, and peripheral edema. All AEs of dermatitis and fatigue for patients treated in the 75 mg BID cohort were considered treatment-related. The majority of AEs were CTCAE grade 1 or 2 in intensity. However, 33/56 of patients experienced at least one CTCAE grade 3 event during the study, of which 18/56 experienced at least one treatment-related AE > Grade 3. The majority of grade 3 events were reported by only one patient. Events that were reported in more than one patient include left ventricular dysfunction, nausea, vomiting, fatigue, febrile infection, lower respiratory tract infection, increased blood alkaline phosphate, GGT increased, hypoxia, dermatitis acneiform, and hypertension. Fatigue was the most commonly reported CTCAE grade 3 or higher AE. The only grade 4 event in the study was a single episode of hypoglycemia.

Eighteen patients had permanent discontinuation of study treatment due to at least one adverse event. Five patients had AEs of fatigue reported as contributing to discontinuation of treatment. Two patients each had AEs of anorexia, vomiting, nausea and LV dysfunction, also reported as being at least partly contributing to discontinuation of study treatment. Seven patients had at least one SAE that was considered treatment-related, with hypertension being the only SAE reported more than once.³⁰

LVEF

Scheduled on-treatment assessments (Week 4 or 8) of LVEF were included in two studies of selumetinib monotherapy to evaluate a possible cardiac etiology for peripheral edema. Small median reductions (<10 percentage points) from baseline were recorded during selumetinib treatment in both studies, although individual patient changes were highly variable (−25 to +19 percentage points). No comparative data are available from these studies. Clinically meaningful reductions in LVEF (≥10 percentage points and to below 55%) in patients receiving selumetinib in combination with chemotherapy have been recorded in two randomized double-blind placebo-

controlled Phase 2 studies with scheduled Week 6 echocardiography assessments (D1532C00006 and D1532C00016). These asymptomatic reductions occurred in 13.6% vs. 7.1% of patients with NSCLC receiving selumetinib or placebo in combination with docetaxel and in 20.5% vs. 11.4% of patients with advanced melanoma receiving selumetinib or placebo in combination with dacarbazine. Evidence of reversibility of LVEF changes on continuing selumetinib (often without therapeutic treatment) has been demonstrated in patients with follow-up assessments available.

Increase in Creatinine Phosphokinase Levels

Increased CPK levels have been reported with MEK inhibitors ³⁸⁻⁴⁰, which may suggest a class effect. Scheduled measurement of CPK levels has not been included in studies of selumetinib. However, AEs of increased CPK levels have been reported in a small number of patients. In study D1532C00006, CPK levels were measured at a single investigational site in patients with melanoma believed by the investigator to be receiving selumetinib + dacarbazine. AEs of increased CPK levels were reported in 7 patients (15.9% of the overall selumetinib + dacarbazine group). CPK levels were not measured in the 3 patients at the same site who received placebo + dacarbazine. A causal relationship between selumetinib and increased CPK levels has not been established.

Muscle Weakness

Neck extensor muscle weakness (with mild increase in CPK levels), reversible on selumetinib interruption, has been reported in 3 patients with uveal melanoma treated with selumetinib in a non-AZ-sponsored study.⁴¹ A relationship between selumetinib and muscle weakness has not been established.

Potential Drug Interactions

In vitro metabolic studies of selumetinib using hepatocytes from humans and animals found that the biologically active N-desmethyl derivative was detected in mouse and human hepatocytes, detected minimally in monkeys, and was not detected in rats.³⁰ CYP3A4 is the predominant isoform responsible for selumetinib oxidative metabolism with CYP2C19, CYP1A2, CYP2C9, CYP2E1 and CYP3A5 involved to a lesser extent. In vitro studies indicate that selumetinib also undergoes direct Phase 2 metabolic reactions to form glucuronide conjugates principally involving the enzymes UGT1A1 and UGT1A3. Cytochrome P450 (CYP)1A2 was the enzyme primarily responsible for the formation of the N-desmethyl derivative. CYP2C19 and CYP3A4 were also minimally involved in the transformation to N-desmethyl metabolite. Neither selumetinib, nor its active metabolite, were found to be inhibitors of CYP isoforms 1A2, 2C8, 2C19, 2D6, or 3A4. At the systemic selumetinib concentrations observed following 100 mg selumetinib capsule formulation in man, no significant cytochrome P450 interactions would be expected. Since the formation of N-desmethyl AZD6244 from selumetinib may occur through the CYP1A2 pathway and smoking induces this pathway, the smoking status of the subjects should to be recorded in all studies (i.e., smoker or non-smoker) to investigate whether smoking status influences systemic drug exposures of N-desmethyl selumetinib.

Selumetinib exposure in subjects of Asian ethnicity

Selumetinib exposure appears to be higher in Japanese, non-Japanese-Asian and Indian healthy adult volunteers compared to Western adult volunteers. However, there is considerable overlap with Western subjects when corrected for body weight or BSA. No specific adjustment to the starting dose is recommended for paediatric Asian patients, however these patients should be closely monitored for adverse events.

Vision Changes

Visual disturbances symptoms, including blurred vision have been reported in 10% of patients during treatment with selumetinib. Adverse events of central serous retinopathy/retinal pigment epithelial detachment have been reported in a small number of patients receiving selumetinib. Rare adverse event of retinal vein occlusion have been reported, however a relationship between selumetinib and retinal vein occlusion has not been established.

Rationale

The preclinical work described above, demonstrating the important role of MAPK pathway activation in NF2-driven tumorigenesis, provides strong rationale for targeting the MAPK signaling pathway through selective therapeutic inhibition of MEK1/2 with selumetinib. Therefore, we are initiating a single institution, Phase 2 trial for patients with neurofibromatosis type 2 (NF2). There will be two strata in this clinical trial. Stratum 1 will include patients with NF2 with VS who exhibit hearing loss. Stratum 2 will include for patients who have progressive lesions other than VS (including non-vestibular schwannomas, meningiomas, and spinal cord lesions). Our hypotheses are: 1) selumetinib given orally twice daily will improve hearing in NF2 patients with VS in stratum 1 and 2) selumetinib given orally twice a day will decrease the size of NF2-associated tumors in stratum 2.

3 PATIENT SELECTION

3.1 Inclusion Criteria:

3.1.1 Patients must have a confirmed diagnosis of neurofibromatosis 2 by fulfilling National Institute of Health (NIH) criteria or Manchester criteria, or by detection of a causative mutation in the NF2 gene.

The NIH criteria includes presence of:

- Bilateral vestibular schwannomas, OR
- First-degree relative with NF2 and **EITHER** unilateral eighth nerve mass **OR** two of the following: neurofibroma, meningioma, glioma, schwannoma, juvenile posterior subcapsular lenticular opacity.

The Manchester criteria includes presence of:

- Bilateral vestibular schwannomas, **OR**
- First-degree relative with NF2 and **EITHER** unilateral eighth nerve mass **OR** two of the following: neurofibroma, meningioma, glioma, schwannoma, juvenile posterior subcapsular lenticular opacity, **OR**
- Unilateral vestibular schwannoma **AND** any two of: neurofibroma, meningioma, glioma, schwannoma, juvenile posterior subcapsular lenticular opacity, **OR**
- Multiple meningiomas (two or more) **AND** unilateral vestibular schwannoma **OR** any two of: schwannoma, glioma, neurofibroma, cataract.
- 3.1.2 Patients do not need to have a histologic diagnosis in order to start therapy but must have measurable disease (in 2 dimensions) on MRI scan to be eligible.

3.1.2.1 For Stratum 1: Patients must have a target VS with the following qualities:

Associated with a word recognition score of < 85% and > 0%

AND

Documented progression defined as: Either progressive hearing loss or progressive tumor growth in last 18 months defined as $\geq 20\%$ increase in volume.

3.1.2.2. For Stratum 2: Patients must not meet the eligibility criteria as stated for Stratum 1 and have a target lesion that has exhibited progression. Progression is defined as: $\geq 25\%$ increase in sum of the products of perpendicular diameters of lesions in the preceding 18 months; any new lesion; or clinical deterioration related to disease.

3.1.3 Patients must be able to swallow capsules

3.1.4 Age:

Patients must be ≥ 3 years to ≤ 45 years of age at start of treatment

3.1.5 Prior Therapy

Since there is no standard effective chemotherapy for patients with NF2 and vestibular schwannomas, meningiomas, or ependymomas patients may be treated on this trial without having received prior medical therapy directed at their VS, meningiomas, or ependymomas.

Since selumetinib is not expected to cause substantial myelosuppression, there will be no limit to number of prior myelosuppressive regimen for these NF2 patients.

Patients must have fully recovered from the acute toxic effects of all prior chemotherapy, immunotherapy, biologic therapy or radiotherapy prior to entering this study except for alopecia.

Myelosuppressive chemotherapy: Patients must have received their last dose of known myelosuppressive anticancer chemotherapy at least three weeks prior to study registration or at least six weeks if nitrosourea.

Biologic agent: Patient must have received their last dose of the biologic agent ≥ 7 days prior to study registration. For biologic agents that have a prolonged half-life, at least three half-lives must have elapsed prior to registration

Monoclonal antibody treatment: At least three half-lives must have elapsed prior to registration

3.1.6 Corticosteroids:

Patients who are receiving dexamethasone or other corticosteroids must be on a stable or decreasing dose for at least 1 week prior to registration. It is recommended that patients be off all steroid therapy or receive the least dose that will control their neurologic symptoms

3.1.7 Prior radiotherapy

 \underline{XRT} : ≥ 6 months must have elapsed if prior XRT to vestibular schwannoma or other tumor.

3.1.8 Stem Cell Transplant or Rescue without TBI:

No evidence of active graft vs. host disease and ≥ 3 months must have elapsed since transplant.

3.1.9 Performance Status:

Karnofsky $\geq 60\%$ for patients > 16 years of age Lansky ≥ 60 for patients ≤ 16 years of age.

3.1.10 Organ Function Requirements

3.1.10.1 Adequate Bone Marrow Function Defined as:

- Peripheral absolute neutrophil count (ANC) $\geq 1500/\mu L$
- Platelet count $\geq 100,000/\mu L$ (transfusion independent, defined as not receiving platelet transfusions within a 7 day period prior to registration)
- Hemoglobin ≥ 9 g/dL (may receive RBC transfusions)

3.1.10.2 Adequate Renal Function Defined as:

- Creatinine clearance or radioisotope GFR ≥ 70ml/min/1.73 m2 or
- A serum creatinine ≤1.5×ULN for age and sex

3.1.10.3 Adequate Liver Function Defined as:

- Bilirubin (sum of conjugated + unconjugated) ≤ 1.5 x upper limit of normal (ULN) for age
- AST(SGOT)/ALT(SGPT) ≤2.5×ULN institutional upper limit of normal for age

3.1.10.4 Central Nervous System Function:

- Patients with seizure disorder may be enrolled if they are receiving non-enzyme inducing anticonvulsants and the seizures are well controlled.

3.1.10.5 Cardiac Function

Adequate cardiac function defined as:

- LVEF \geq 55% by ECHO
- QTc interval <450 msecs by EKG

3.1.10.6 Hypertension

- Patients, 3 to < 18 years of age must have a blood pressure that is \le 95th percentile for age, height and gender at the time of registration.
- Patients who are ≥18 years of age must have a blood pressure that is <140/90 mm of Hg at the time of registration.

Patients may be on blood pressure medication provided that it is not on the contraindicated list and that the medication has not been adjusted in the previous 3 months.

3.1.11 Growth factors:

All colony forming growth factor(s) have been discontinued for at least one week prior to registration (filgrastim, sargramostim, and erythropoietin). For patients on long acting growth factors, the interval should be two weeks.

3.1.12 Inclusion of Women and Minorities

Both males and females of all races and ethnic groups are eligible for this study.

3.1.13 Informed Consent:

All patients and/or their parents or legal guardians must sign a written informed consent. Assent, when appropriate, will be obtained according to institutional guidelines.

3.2 Exclusion Criteria

3.2.1 Pregnant or breast-feeding women will not be entered on this study due to risks of fetal and teratogenic adverse events as seen in animal/human studies. The effects of selumetinib on the developing human fetus are unknown. For this reason, women of child-bearing potential and men must agree to use adequate contraception (hormonal or barrier method of birth control; abstinence) prior to study entry and for the duration of study participation, and for four weeks after dosing with selumetinib ceases. The selumetinib manufacturer recommends that adequate contraception for male patients should be used for 16 weeks post-last dose due to sperm life cycle. Women of child-bearing potential must have a negative pregnancy test prior to study registration. Should a woman become pregnant or suspect she is pregnant while she or her partner is participating in this study, she should inform her treating physician immediately.

Note: Female subjects are considered "of child-bearing potential" if they are anatomically and physiologically capable of becoming pregnant. For girls of normal reproductive potential, the possibility of becoming pregnant requires ovulatory menstrual cycles and heterosexual intercourse. Although the timing of ovulation relative to menarche is variable, there is consistent evidence that some girls may have ovulatory cycles prior to menarche, and that, in healthy populations, regular ovulation may begin within a few months of menarche. Therefore, menarche is the most feasible clinical indicator of the biological potential for pregnancy.

Male patients with sexual partners who are pregnant or who could become pregnant (i.e. women of child-bearing potential) must use acceptable, effective and reliable methods of contraception during the study and for at least 12 weeks after the last dose of selumetinib or for longer if required, depending on the prescribing information of the combination or concomitantly administered medications.

- 3.2.2 Patients with any clinically significant unrelated systemic illness (serious infections or significant cardiac, pulmonary, hepatic or other organ dysfunction) that is likely to interfere with the study procedures or results
- 3.2.3 Patients who are currently receiving another investigational drug within 4 weeks prior to the first dose of study treatment, or within a period during which the investigational drug or systemic anticancer treatment has not been cleared from the body (e.g. a period of 5 'half-lives'), whichever is the most appropriate and as judged by the investigator are not eligible.

- 3.2.4 Patients who have taken another BRAF inhibitor such as Vemurafenib or Dabrafenib prior to study registration are not eligible. Prior treatment with selumetinib or another MEK inhibitor is not allowed.
- 3.2.5 Patients with QTc interval of > 450 msec
- 3.2.6 Patients who require enzyme inducing anti-convulsants to control seizures.
- 3.2.7 Anticoagulation: Patients receiving coumadin are eligible but must have their PT and INR monitored prior to each 4 week course.
- 3.2.8 Patients who in the opinion of the investigator may not be able to comply with the safety monitoring requirements of the study are not eligible.
- 3.2.9 Patients with the following cardiac conditions:
 - a. Uncontrolled hypertension in adults (BP \geq 140/90 mmHg despite medical therapy)
 - b. Acute coronary syndrome within 6 months prior to starting treatment
 - c. Uncontrolled Angina Canadian Cardiovascular Society grade II-IV despite medical therapy (Appendix H)
 - d. Symptomatic heart failure NYHA Class II-IV, prior or current cardiomyopathy, or severe valvular heart disease (Appendix I)
 - e. Prior or current cardiomyopathy including but not limited to the following:
 - i. Known hypertrophic cardiomyopathy
 - ii. Known arrhythmogenic right ventricular cardiomyopathy
 - f. Previous moderate or severe impairment of left ventricular systolic function (LVEF <45% on echocardiography or equivalent on MuGA) if known even if full recovery has occurred.
 - g. Severe valvular heart disease
 - h. Baseline Left ventricular ejection fraction (LVEF) below the LLN or <55% measured by echocardiography or institution's LLN for MUGA
 - i. Atrial fibrillation with a ventricular rate >100 bpm on ECG at rest
- 3.2.10 Ophthalmological conditions as follows:
 - a. Current or past history of retinal pigment epithelial detachment (RPED)/central serous retinopathy (CSR) or retinal vein occlusion
 - b. Intraocular pressure (IOP) > 21 mmHg or uncontrolled glaucoma (irrespective of IOP) as defined by ophthalmologist
- 3.2.11 Major surgery within 4 weeks of starting selumetinib. Portacath insertion, G Tube placement, and insertion of ventriculoperitoneal shunt are not considered major surgeries.
- 3.2.12 History of allergic reactions attributed to compounds of similar chemical or biologic composition to selumetinib or combination medications or any excipient of these medicinal products
- 3.2.13 History of a medical or psychiatric illness, that in the investigator's judgment renders the patient incapable of further therapy on this protocol

3.2.14 Patients with progressive disease associated with significant or disabling clinical symptoms requiring immediate intervention with surgery or radiation therapy are not eligible.

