4.3 Patient Registration

Patients must be registered prior to any protocol treatment. Patient registration is only available to authorized personnel at CCHMC. Signing off of the eligibility checklist by Investigator or sub-Investigator completes registration.

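### Section 3.2.1 requires 12 weeks of post-dose contraception for men with partners at risk, 4 weeks less than the 16-week advice it cites, and gives no reason

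*Combined protocol and SAP*

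**What the plan says.** All three statements stand in section 3.2.1 (Exclusion Criteria), which excludes pregnant and breast-feeding women "due to risks of fetal and teratogenic adverse events as seen in animal/human studies".

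1. **Opening agreement.** The text says that "women of child-bearing potential and men must agree to use adequate contraception" before entry, while on study, and "for four weeks after dosing with selumetinib ceases". No partner condition is attached to men here.
2. **Manufacturer's advice.** The next sentence reports a recommendation that "adequate contraception for male patients should be used for 16 weeks post-last dose due to sperm life cycle".
3. **Male-patient paragraph.** After a note on child-bearing potential in female subjects, a separate paragraph begins "Male patients with sexual partners who are pregnant or who could become pregnant" and obliges these men to use "acceptable, effective and reliable methods of contraception during the study and for at least 12 weeks after the last dose of selumetinib". It continues "or for longer if required, depending on the prescribing information" of combination or concomitant medicines.

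No other section sets a contraception period for men. The 12 weeks in section 5.1 concerns blood donation only.

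**The concern.** The criterion rests on fetal risk. It cites a period that is specific to this drug and to men, gives the biological reason for it, and then sets a shorter binding minimum without comment. A man with a partner at risk can follow the binding rule exactly and still stop before the date that the same criterion reports as advised. The reader gets a reason for 16 weeks and none for 12. Section 2.2.1 also reports that selumetinib increased micronucleated immature erythrocytes in mice, mainly by an aneugenic route. That does not establish a risk through the father, but it is a reason not to leave the interval unexplained.

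A smaller matter is the opening sentence. It includes men, its only post-dose figure is four weeks, and it does not direct them to the longer rule further down.

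What is at stake is the protection of partners and pregnancies, and clarity of instruction. Nothing statistical depends on it.

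**Working it through.** There is no design figure to reproduce: the periods are stated outright and the section gives no derivation of the 12 weeks.

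**Inputs, all from section 3.2.1**

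| Statement | Applies to | Force | Weeks | Days |
|---|---|---|---|---|
| Opening agreement | Women of child-bearing potential; all men | Mandatory | 4 | 28 |
| Male-patient paragraph | Men with a partner at risk | Mandatory minimum | 12 | 84 |
| Manufacturer's advice | Male patients | Recommendation | 16 | 112 |

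**Step 1: binding male floor against the cited advice.** 112 − 84 = 28 days (4 weeks). The floor is 84/112 = 75% of the advised period.

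**Step 2: does the extension clause close the gap?** The 12 weeks can lengthen, but only on the labelling of other medicines. The 16-week selumetinib advice is not named as a trigger. Section 5.4.8 bars other anti-cancer or experimental agents, so the part of the clause about combination medicines has little to act on.

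**Step 3: does time on study close the gap?** The male rule also runs during the study, and section 5.6 plans two years of monitoring after treatment (about 104 weeks, which exceeds 16). If follow-up counts as being on study, men who remain in it are covered beyond 16 weeks. Men who leave early are not. Under section 5.7.5, a patient removed for progression is observed for 30 days after the last dose. Since 30 < 84, the 12-week floor governs him, and the 28-day shortfall remains. Withdrawal of consent (5.7.3) and new anti-cancer therapy (5.7.6) can also end participation early.

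**Step 4: opening figure against the male floor.** 84 − 28 = 56 days (8 weeks). A man with a partner at risk is subject to both mandatory periods, and the longer controls: max(28, 84) = 84 days. The text therefore never permits him to stop at day 28. The fault is a missing cross-reference.

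**Step 5: how many patients?** Section 13.2 plans two strata of 9 + 8, so 2 × 17 = 34 patients of both sexes at most. The documents do not say how many would be men with a partner at risk.

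**The case against.** The strongest reply is that a mandatory floor with a longer recommendation is coherent. The 16-week advice is printed in the criterion, addresses male patients generally, and is compatible with a rule worded as a minimum. A man can satisfy both, and nothing says that the advice is declined. This stands as far as it goes: there is no contradiction. But the advice is reported without being required, and the reader cannot tell whether the difference is deliberate.

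A second reply is that the manufacturer's source is not available, so the documents cannot settle whether 12 or 16 weeks is right. That also stands, and it is why the change is made subject to confirmation.

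A third is that two-year follow-up already covers many men. This holds only if follow-up counts as study time, and not for men who leave early.

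Two stronger readings are tempting and should be resisted. A reader might infer that the four-week sentence releases men with partners at risk at four weeks. It does not, because the male-patient paragraph in the same criterion binds them to 12. A reader might also infer that four weeks is what men confirm at registration, since section 4.3 says "Signing off of the eligibility checklist by Investigator or sub-Investigator completes registration". Neither the checklist nor the consent form was available, and nothing can be concluded about which period they state.

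**Conclusion.** The point holds as a gap in the binding rule for men with partners at risk: the mandatory minimum is 28 days below the advice that section 3.2.1 itself cites with a biological reason, and no reason is given for the lower figure. The four-week wording for men is secondary and a matter of drafting.

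The conclusion assumes that the 16-week figure is correctly reported. Its practical reach depends on how long each man counts as on study; it is clearest for those who leave before 12 weeks have passed. The number affected is unknown. The documents do not show that 12 weeks is unsafe, only that it is unexplained. This is a cheap improvement for patient safety, with no effect on endpoints, analysis or error rates.

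**What to change.** - **Male-patient paragraph of 3.2.1:** raise the minimum from 12 to 16 weeks after the last dose, once the manufacturer confirms the figure. Keep the partner condition and the extension for other medicines. The partner condition matters because entry is from age 3 (section 3.1.4), and a 16-week duty on every male patient would serve no purpose.
- **Opening sentence:** limit the four-week post-dose period to women of child-bearing potential, and refer men to the male-patient paragraph for theirs.
- **Manufacturer sentence:** keep it as the stated reason for the male period.
- **If the sponsor prefers 12 weeks:** say that 12 weeks governs and why the longer advice is not adopted.
- **Consent form and eligibility checklist:** check that they match.

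**Cost.** Men with partners at risk carry 28 more days of contraception (84 to 112 days, 28/84 = +33%). Men outside the partner condition would no longer have a stated four-week period. Women stay at 28 days. The remainder is wording in the protocol, consent form and checklist.
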